Guanfacine is the oldest alpha-2 adrenergic agonist in clinical use in this class.²⁴ Of the alpha-2 agonists, guanfacine has the lowest rate of sedation. 25 Guanfacine is currently approved in tablet form for the treatment of hypertension (1 to 2 mg) and Attention Deficit Hyperactivity Disorder (1 to 4 mg). Guanfacine is readily absorbed with around 80% oral bioavailability and has an elimination half-life of ~17 h with renal excretion accounting for ~50%. Guanfacine has been shown to have similar in vitro potency as clonidine to inhibit conduction in rat sciatic nerve fibers.²⁷ Intrathecal guanfacine has a similar antinociceptive effect as that of intrathecal clonidine in a goat model.²⁸ Guanfacine showed longer antinociceptive effect in comparison to clonidine (8 h vs. 5 h) due to slower elimination of guanfacine from spinal cord tissue. In a rat model, intrathecal guanfacine has shown antinociceptive effect for greater than 18 h (both 25 mcg and 50 mcg) in comparison to clonidine injection (50 mcg) which declined to baseline within 4 h.²⁹ This study also reported a lower rate of elimination of guanfacine from spinal cord tissue compared to clonidine. Highly concentrated guanfacine (75 mcg in 15 µl saline) solution administered through an intrathecal route has been shown to be nontoxic in the subarachnoid space, establishing the safe use of guanfacine for perineural blockade.³⁰ Guanfacine as studied in animals and used in humans has a safe risk profile, suggesting that repurposing it for other indications. Guanfacine has the potential to be developed as a safe, non-opioid, analgesic for acute and chronic debilitating pain. Guanfacine in combination with 1% lidocaine is expected to be safe and to provide an extended duration of pain relief in painful trigeminal neuropathy patients who are not able to obtain pain relief from standard neuropathic pain medication.

PheWAS data indicating the role of the alpha-2-adrenergic receptor in trigeminal nerve pain

BioVU is a large repository of de-identified DNA samples that Vanderbilt University Medical Center (VUMC) has cataloged for >10 years from what otherwise would have been excess, discarded patient blood samples collected during routine clinical testing. Biospecimens within BioVU are linked to corresponding longitudinal clinical and demographic data derived from the Synthetic Derivative, our de-identified database of EMRs. 31-33

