2.0 STUDY DESIGN

Primary Hypothesis:

Due to its different but relevant mechanism of action, guanfacine will be an effective adjunct to lidocaine in trigeminal nerve block for the treatment of painful trigeminal neuropathy by enhancing and prolonging pain relief compared to lidocaine alone.

Endpoints

The following endpoints will be measured to evaluate the exploratory objectives of the study assessing guanfacine and lidocaine in combination compared to lidocaine alone, in pain management in the painful trigeminal neuropathy patient.

- Primary endpoint: time to return to baseline pain (VAS) measurement after treatment with guanfacine as adjuvant to 1% lidocaine compared to 1% lidocaine alone
- Safety endpoint: comparable side effect profile of combination product compared to lidocaine alone on relevant adverse event measures: sedation, local site reaction, confusion
- Secondary endpoint: pain intensity after treatment to be measured throughout the follow-up periods on a visual analog scale (VAS)
- Secondary endpoint: quality of life after treatment to be measured using PROMIS Global Health -10 SF during the follow-up periods
- Secondary endpoint: frequency of acute trigeminal nerve pain attacks during the follow-up periods
- Secondary endpoint: total amount of rescue medications (opioid and non-opioid analgesics) for pain management during the follow-up periods
- Secondary endpoint: time to first rescue medication during the follow-up periods

Experimental Design

The trial is designed as a single-center, randomized, double-blind, controlle, 2x2 crossover pilot study with two arms: study drug (guanfacine and lidocaine combination) and active control (lidocaine alone). The target sample size is 30 study drug vs. 30 active control.

Not all participants that are randomized and initiate the first arm of the trial will *necessarily* complete *both* arms of the crossover trial. Based on previous experience, initiating the first arm of the cross over trial in 40 participants should be sufficient reach the full sample size (30 study drug vs. 30 active control). The trial will be complete and enrollment will cease upon reaching the full proposed sample size (30 study drug vs. 30 active control).

Approximately 80 patients meeting preliminary enrollment criteria will be consented for screening with the goal of roughly half being eligible to randomize and begin participation in the trial.

Inclusion Criteria

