3.0 DRUG PRODUCTS

Study drug: Lidocaine 1% PF vials will be purchased from Pfizer. API grade guanfacine will be purchased from Procos S.p.A., and Vanderbilt University Medical Center's Investigational Drug Service will compound and dispense a 10 ml sterile syringe with a sterile locking syringe cap containing 6 ml 1% lidocaine with 250 mcg guanfacine (see **Appendix A** for mixing instructions).

Active control: The active control drug (6 ml 1% lidocaine sterile injection) will be dispensed by VUMC's Investigational Drug Service and will be identical in appearance to the study drug.

Mode of administration: Trigeminal nerve block procedure

Trigeminal nerve block will occur with the patient supine in the procedure suite. Based upon landmark and fluoroscopic image, the needle insertion site will be located and infiltrated with 1ml of 1% lidocaine. A 22-gauge stimuplex needle will be advanced under fluoroscopic guidance to the pterygoid fossa. Active stimulation at 0.75 mV will be used to confirm needle tip approaching the V2 maxillary branch of the trigeminal nerve and reduced to 0.3mV upon patient sensation. After confirming that the needle tip is in position with no sensation felt by the patient at <0.3mV, and after negative aspiration for blood or cerebral spinal fluid (CSF), 0.25ml of iodinated contrast (Omnipaque 300) or gadolinium-based contrast agent (Omniscan) if allergic to iodinated contrast will be injected under digital subtraction fluoroscopy to ensure no vascular uptake. If vascular uptake occurs, the needle tip will be adjusted, and tested again for vascular uptake. After confirmation of the needle placement, 3ml of the study drug or active control will be delivered. The needle will be retracted and angled toward the V3 mandibular branch of the trigeminal nerve and confirmed in the same method with fluoroscopy and stimulation as above. After confirmation of needle placement, the remaining 3ml of the study drug or active control will be deposited. The needle will then be removed. The patient will be taken to the recovery room and monitored for 60 minutes.

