Participants will be asked to record their pain intensity, 24- hour VAS and current VAS, before the procedure to establish a baseline pain score. Other data will be collected for secondary measures: frequency of pain attacks, basal and breakthrough opioid and non-opioid analgesic frequency and dose. Overall quality of life (PROMIS Global-10 short form) will be assessed.³⁹ Women of childbearing potential will undergo a urine pregnancy test prior to receiving the nerve block.

First trigeminal nerve block procedure: Participant will receive either study drug (guanfacine and lidocaine combination) or active control (lidocaine alone) for the trigeminal nerve block based on randomization. Participants will be monitored for pain intensity at 30-minute time intervals for the first 8 hours after block in addition to safety monitoring procedures. Participant responses will be collected at 30 minute intervals for the first 8 hours while in the recovery (first 60 minutes) and after discharge home, with responses allowed all the way until the next time point and actual time of the response being used in analysis. Assessments will be recorded according to the patient's preference, either on paper or via text message) using the Twilio application linked to REDCap. Patients will also receive a sheet with contact information for the study nurse.

First follow-up period (Day 2 to Day 14)

Participants will be monitored once daily at approximately the same timepoint for 14 days using text message generated using the Twilio application or recorded on a paper diary. Participants will also be monitored for any use of rescue medication (analgesics) once daily. The study nurse will monitor participants once weekly for overall quality of life via phone call using the PROMIS global 10 SF. Participants will be instructed to contact the study nurse with any adverse events directly by phone.

At the end of the first follow-up period, participants will be contacted for crossover to the other arm to receive the second trigeminal nerve block using the alternative drug (study drug or active control), not received during the first nerve block. At the second study visit, participants will record 24-hour VAS and current VAS, and the PROMIS Global-10 Short Form to establish baseline measurement again. Women of childbearing potential will undergo a urine pregnancy test prior to receiving the nerve block.

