6.0 RISKS

During the consent process, study personnel will address potential discomfort and risks associated with the protocol. These will be included in the consent form.

Based on the known common side effects of the study drugs and the trigeminal block procedure, the following risk associated with participation in the study are perceived as low:

- Bradycardia
- Hypotension
- Dry Mouth
- Sedation
- Dizziness
- Headache
- Bruising, redness, itching, or swelling at the site of injection
- Intravascular injection resulting in seizure or stroke
- Bleeding
- Increased pain

In the event sedation or dizziness is observed after the procedure, standard of care practices for managing side effects will be performed, and the event will be documented and recorded according to the regulation.

It is understood that there may be as-yet unknown or unanticipated adverse effects of this study treatment. The study team will continually monitor for these effects and consider altering the protocol if needed to ensure patient safety. Changes in the procedures of the study, as well as any change(s) in the risks and/or benefits will be presented to and discussed with the subjects upon approval from the appropriate regulatory bodies for implementation of such revision(s).

Safety Monitoring:

Patients are examined on the day of the procedure to confirm the source of pain, vital signs are stable and in normal range, and female patients are confirmed not-pregnant through point of care pregnancy tests. During the procedure continuous pulse oximetry is used to monitor oxygenation, blood pressure is obtained every 2 minutes, and 3-lead electrocardiogram is monitored for heart rate and rhythm. Following the procedure, patients are taken to the recovery room adjacent to the procedure room to be monitored for 1 hour with continuous pulse oximetry, blood pressure (measured every 5 minutes), and continuous ECG to ensure stable vital signs. The patients are discharged home with a responsible adult after recovery. Before, during, and after the procedure patients are monitored by a registered nurse skilled in the evaluation of vital signs and familiar with the procedure. [name] is an Anesthesiologist and will be present for the duration of patient care.

Data Monitoring:

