The Principal Investigator will determine the relationship of each SAE to study drug (i.e., causality) by using the classification criteria 'not related,' 'possibly related', or 'probably related'. Descriptions of the three classification categories are as follows:

Not Related

Exposure to study drug has not occurred; administration of study drug and the adverse event are not reasonably related in time; or the SAE is considered by the Investigator to be due to a pre-existing condition, a known manifestation of the target disease, a recurrent condition, or is likely explained by environmental or diagnostic therapeutic factors or was pre-existing and did not deteriorate.

Possibly Related

The SAE occurred during or within a reasonable period of time after administration of the study drug, or a preexisting event worsened within an appropriate period of time after administration of study drug, but the SAE

could be explained equally well by factors or causes other than exposure to the study drug. This category will also be used if there is a lack of information, or insufficient or conflicting evidence exists for classifying the causality of the SAE.

Probably Related

The SAE occurred during or within a reasonable period of time after administration of the study drug or a preexisting event worsened within an appropriate period of time after administration of study drug, and at least one of the following criteria is applicable:

- the event could not be explained by the clinical condition or history of the subject, environmental or toxic factors, or other diagnostic or therapeutic measures;
- the event was an expected ADR associated with study treatment or a class-labeled drug effect;
- the SAE subsided or disappeared after withdrawal or dose reduction of study treatment; or
- the SAE recurred after re-exposure to study treatment.

Adverse Event Recording

Each adverse event occurring to a subject, either spontaneously revealed by the subject or observed by the Investigator, whether believed to be related or unrelated to the study drug, must be recorded on the AE Case Report Form and the subject's file.

Adverse Event Reporting

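### After the 60-minute recovery no scheduled contact is specified to ask about adverse events, so later sedation and confusion are likely to be under-recorded

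*Combined protocol and SAP*

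**What the plan says.** - Section 2.0, Endpoints, defines the safety endpoint as "comparable side effect profile of combination product compared to lidocaine alone on relevant adverse event measures: sedation, local site reaction, confusion".
- Section 3.0 on the block procedure: "The patient will be taken to the recovery room and monitored for 60 minutes". Section 6.0, Safety Monitoring, gives the content of that hour: patients are "monitored for 1 hour with continuous pulse oximetry, blood pressure (measured every 5 minutes), and continuous ECG to ensure stable vital signs". A registered nurse attends, and sedation or dizziness seen after the procedure is to be recorded. No sedation or confusion scale is named there or elsewhere.
- Section 5.0, Study Visit 2: "Participants will be monitored for pain intensity at 30-minute time intervals for the first 8 hours after block in addition to safety monitoring procedures".
- Section 5.0, both follow-up periods: a daily text or diary entry, with "Participants will also be monitored for any use of rescue medication (analgesics) once daily", and a weekly nurse call for quality of life. The schedule also places attack frequency in follow-up.
- On adverse events, both follow-up periods say: "Participants will be instructed to contact the study nurse with any adverse events directly by phone".
- Section 7.0, Adverse Event Recording, covers each event "either spontaneously revealed by the subject or observed by the Investigator".
- The schedule in Section 5.0 marks Adverse Events at both procedures and in both follow-up periods. It attaches no collection method to the row.
- Section 7.0, Safety Stopping Criteria, stops enrollment for an interim review if sedation exceeds expectation, in severity or duration, in at least 20% of patients in either group.

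**The concern.** The events of interest can fall where nobody is specified to ask. Section 7.0 puts the typical course of lidocaine effects at 2 hours, says the risks of the block and of lidocaine must be told apart from guanfacine's, and expects guanfacine to add drowsiness, dizziness and tiredness. Section 1.0 says guanfacine "has an elimination half-life of ~17 h". The hours that best separate the two treatments therefore come after discharge.

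Two things are at stake. First, the endpoint is worded as comparability, and missed events make the arms look more alike. Second, one limb of the sedation rule is duration, and duration beyond the recovery hour is known only if the participant reports it.

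**Working it through.** **The plan's own figures.** The documents give no figure for the safety endpoint or for the operating characteristics of the sedation rule. Their one computed figure, about 90% power for the primary endpoint, reproduces: the noncentrality is 30 × 28² / (2 × 30²) = 13.07, which gives 0.909 for the two-degree-of-freedom test. It has no bearing on this point.

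**Step 1: what each contact asks.**

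| Contact | Stated content | Adverse-event question stated? |
|---|---|---|
| Recovery, 0 to 60 min | Oximetry, blood pressure, ECG, nurse observation | No, but events can be observed |
| Prompts every 30 min to 8 h | Pain intensity | No |
| Daily text or diary | Pain, rescue medication | No |
| Weekly nurse call | PROMIS, attack frequency | No |
| Procedure 2, at least 15 days after Procedure 1 | Adverse Events marked | Method not stated |

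The first weekly call comes at about 7 × 24 = 168 h. That is 168 / 17 = 9.9 of the quoted half-lives, so anything volunteered then is a recollection.

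**Step 2: how much could be lost.** Let f be the share of events that appear only after discharge and m the share of those that are not volunteered. The share recorded is c = 1 − f × m. The loss applies only to events after discharge. Both f and m are assumptions, since the documents give neither.

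| | m = 25% | m = 50% | m = 75% |
|---|---|---|---|
| f = 25% | 0.94 | 0.88 | 0.81 |
| f = 50% | 0.88 | 0.75 | 0.63 |
| f = 100% | 0.75 | 0.50 | 0.25 |

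**Step 3: effect on the comparison.** Take assumed true rates of 30% and 10% and the same c in both arms. Power is for 30 per group and ignores the pairing.

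| c | Recorded rates | Difference | Power |
|---|---|---|---|
| 1.00 | 30% vs 10% | 20 points | 0.49 |
| 0.75 | 22.5% vs 7.5% | 15 points | 0.37 |
| 0.50 | 15% vs 5% | 10 points | 0.25 |
| 0.25 | 7.5% vs 2.5% | 5 points | 0.14 |

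The ratio stays at 3. The absolute difference and the power shrink.

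**Step 4: effect on the sedation rule.** At 30 patients per group, 20% is 0.20 × 30 = 6. With an assumed true rate p of qualifying sedation, the chance that the recorded count reaches 6 is P(X ≥ 6), with X binomial (30, p × c).

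| p | c = 1.00 | c = 0.75 | c = 0.50 | c = 0.25 |
|---|---|---|---|---|
| 20% | 0.57 | 0.29 | 0.07 | 0.003 |
| 30% | 0.92 | 0.70 | 0.29 | 0.02 |
| 40% | 0.99 | 0.92 | 0.57 | 0.07 |

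The two right-hand columns need most or all events to arise after discharge: c = 0.50 requires f of at least 0.67 if m is no more than 75%, because f = 0.50 / 0.75.

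**The case against.** Spontaneous reporting plus observation is a recognised method, and this is a pilot. The call script and case report form are not in the documents and may already contain an adverse-event question. The Section 5.0 wording about safety monitoring procedures during the first 8 hours could be read as covering the time at home. Patients leave with a responsible adult, and the team reviews adverse events every two weeks.

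Part of this stands: under-recording is likely, not demonstrated. The rest does not close the gap. The only section headed Safety Monitoring describes nothing after discharge. The accompanying adult is given no reporting task. The team meetings review what has already been recorded.

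Four stronger readings are tempting, and the documents do not support them:

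- *Events count only if the participant phones.* Section 7.0 also accepts anything volunteered or observed, so a mention on a weekly call or at Procedure 2 counts, and the schedule marks adverse events in those periods.
- *The sedation rule has no input.* Sedation in the recovery hour is observed and recorded. The rule's own response to oversedation in one group, longer monitoring until recovery, suggests that it is at least partly about that hour. The weak part is duration, or onset, after discharge.
- *The loss is larger in the arm that sedates.* This would follow if sedated people called less, or if guanfacine events came later. The documents give no reporting or timing data by arm, and the trial is double-blind. The half-life is quoted alongside oral bioavailability and is not a duration of sedation. Section 1.0 also says guanfacine has the lowest sedation rate among the alpha-2 agonists.
- *A true 20% rate would be recorded as 10%.* That needs half of all events to be lost, including those in the observed hour. If half appear in recovery and half of the rest go unreported, 20% becomes 20% × 0.75 = 15%.

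**Conclusion.** The point holds as a weakness in data collection. After discharge no adverse-event question is specified at any of the prompts, daily contacts or weekly calls, so sedation and confusion that begin or persist at home depend on being volunteered. Even equal under-recording in both arms moves the absolute difference toward the comparability that the endpoint describes, and it weakens the duration limb of the sedation rule.

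The size is unknown. Over the assumed ranges (25% to 100% of events after discharge, 25% to 75% of those not volunteered) the share recorded runs from 25% to 94%. The result rests on the contacts asking only what the protocol says they ask. A call script or form that already solicits adverse events would reduce the point to a missing description.

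**What to change.** Use the contacts that already exist, identically in both periods:

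- Add a brief dated item on sedation, confusion and site reaction to some of the day-of-procedure prompts. Hourly would mean 8 of the 16. Place it after the pain score, so that the primary-endpoint response comes first.
- Add the same item to the daily text or diary.
- Add one scripted adverse-event question to the weekly nurse call.
- State this method against the Adverse Events row of the schedule, and in Section 7.0, Adverse Event Recording.

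This changes data collection only. The sedation rule and the recovery monitoring stay as written. The cost is a REDCap form edit, a diary line and a line in the call script. The downside is slightly longer prompts, with a small risk of non-response.

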6.0 RISKS

During the consent process, study personnel will address potential discomfort and risks associated with the protocol. These will be included in the consent form.

Based on the known common side effects of the study drugs and the trigeminal block procedure, the following risk associated with participation in the study are perceived as low:

- Bradycardia
- Hypotension
- Dry Mouth
- Sedation
- Dizziness
- Headache
- Bruising, redness, itching, or swelling at the site of injection
- Intravascular injection resulting in seizure or stroke
- Bleeding
- Increased pain

In the event sedation or dizziness is observed after the procedure, standard of care practices for managing side effects will be performed, and the event will be documented and recorded according to the regulation.

It is understood that there may be as-yet unknown or unanticipated adverse effects of this study treatment. The study team will continually monitor for these effects and consider altering the protocol if needed to ensure patient safety. Changes in the procedures of the study, as well as any change(s) in the risks and/or benefits will be presented to and discussed with the subjects upon approval from the appropriate regulatory bodies for implementation of such revision(s).

Safety Monitoring:

Patients are examined on the day of the procedure to confirm the source of pain, vital signs are stable and in normal range, and female patients are confirmed not-pregnant through point of care pregnancy tests. During the procedure continuous pulse oximetry is used to monitor oxygenation, blood pressure is obtained every 2 minutes, and 3-lead electrocardiogram is monitored for heart rate and rhythm. Following the procedure, patients are taken to the recovery room adjacent to the procedure room to be monitored for 1 hour with continuous pulse oximetry, blood pressure (measured every 5 minutes), and continuous ECG to ensure stable vital signs. The patients are discharged home with a responsible adult after recovery. Before, during, and after the procedure patients are monitored by a registered nurse skilled in the evaluation of vital signs and familiar with the procedure. [name] is an Anesthesiologist and will be present for the duration of patient care.

Data Monitoring:

The PI and study coordinator will be responsible for real-time monitoring of all trial-related activities. [name] will assure that the study is conducted according to Good Clinical Practice Guidelines and according to FDA requirements. The study team will meet bi-weekly to review recruitment, enrollment, retention, status of each participant currently enrolled, adverse events. Targets will be established for enrollment and completion and reviewed at each meeting where strategies will be discussed to assure that the study is on track. Enrollment tables will be developed by the coordinator and project manager for review at team meetings. Adverse and serious adverse events reports will be monitored in real-time by the PI, project manager, and study coordinator. All final

data will be stored on case report forms in REDCap with all source documents uploaded into REDCap then shredded.

All study data, including those captured from the EHR and other hospital databases, will be transferred into the study database via standardized electronic case report forms (eCRFs) which will reside in a centralized REDCap database located on Vanderbilt's secure servers. REDCap is a secure, web-based application for building and managing online databases. Vanderbilt University, with collaboration from a consortium of institutional partners, including the Vanderbilt Institute for Clinical and Translation Research (VICTR) Informatics Core, developed and manages a software toolset and workflow methodology for electronic collection and management of research and clinical trial data. All study data will be entered via a password protected, study unique REDCap database website. REDCap servers are housed in a local data center at Vanderbilt and all web-based information transmission is encrypted. REDCap was developed specifically around HIPAA Security guidelines and is recommended by both the Vanderbilt University Privacy Office and Institutional Review Board. REDCap has been disseminated for use locally at other institutions and currently supports more than 2,700 academic/non-profit consortium partners and over 657,000 research end-users (www.project-redcap.org). Data will be accessed via password protected and secured Web-based interface for data entry and data cleaning. REDCap contains an audit trail for tracking all activities within the system.

To ensure data is accurately and completely collected during the study, periodic monitoring will occur by the Project Manager to ensure the study protocol is being followed, protocol changes have been implemented appropriately, data are being captured per protocol, and are accurate, complete, and current for study subjects. Per best practice guidelines, the monitor will compare a representative number of subject records and other supporting documents with the investigator's reports. Specifically, monitoring activities will include:

- [1] A **Technical Review** annually which will consist of the Project Manager examining the quality and accuracy of data, regulatory documents, and other essential documents. Data quality and accuracy will be reviewed through a CRF data and source document review. The Project Manager will randomly select a pre-determined number of study participants to serve as a representative sample. Regulatory Document Review will consist of a review of IRB approvals, informed consents, critical documents, and protocols/amendments.
- [2] The **Scientific Review** will occur biennially and will consist of a review of the study's organizational structure, patient recruitment, staff training, and quality control procedures by the Project Manager. Site monitoring progress reports will be submitted to the DSMB and other regulatory bodies (IRB, FDA and NIH) as requested and/or required. This Monitoring Plan will serve as a method for identifying systematic problems and provide a means in which to institute resolution and follow-up and therefore increase data quality.

Any omissions and corrections to data submitted to REDCap are noted and queries are generated by the Project Manager or by REDCap's automated system. Data are checked and verified by the Project Manager. A green check is placed beside items that have been verified as accurate when compared to source documentation. For those items that are not initially verified, a query will be issued using the Data Quality Tool in REDCap. Users will then be able to pull up a list of queries using the Resolve Issues Application. Queries will be responded to directly on each respected eCRF page. Furthermore, there is an option to upload additional documentation if requested by the Project Manager. Once a query has been answered, the Project Manager will review the new information and choose to either re-query the data point or close the query by verifying that the data point is complete and accurate. Once all data points on the eCRF page have been reviewed and verified as accurate, a green verification check will be placed at the bottom of the page and the page will be locked, to show that the data on the page is acceptable and ready to be signed off on by the Principal Investigator. If a data point is revised after it was verified and accepted as accurate by the Project Manager then a red exclamation mark will appear

beside the data point. The Project Manager will be notified via the Data Quality Application and will have the option to issue a new query regarding the change or to verify the new data as accurate and complete. All queries will be stored in REDCap's logging and audit trail so that all data revisions are tracked and permanently recorded in order to verify data accuracy. The audit trail will contain a time stamped record of revisions and data entry within the database. All data points entered for the first two patients enrolled at each site will be thoroughly monitored. Thereafter, specific data points that support the primary and secondary endpoints (ex. Inclusion/Exclusion criteria, informed consent, and randomization strata) will be thoroughly reviewed by a Project Manager. 20% to 100% of all additional data points will then be randomly monitored for accuracy. Queries will be issued no later than one month after completed eCRF pages are reviewed. Review will be expedited in cases of urgent concern. Open queries must be answered within 14 calendar days.

All data entered into the REDCap system must come from an original source. Study coordinators will upload all related source documents and medical records that contain information (including Protected Health Information for verification purposes) used in completing the eCRFs into the secure REDCap system. If original source is given verbally and/or if study procedures were documented outside of the medical record, an original source document must be created (which includes applicable signatures and dates) that provides an accurate account of the information that was exchanged. All applicable study source documentation will be uploaded into REDCap for monitoring purposes then shredded.

7.0 REPORTING OF ADVERSE EVENTS OR UNANTICIPATED PROBLEMS INVOLVING RISK TO PARTICIPANTS OR OTHERS

Adverse Event

An AE is "any untoward medical occurrence in a patient or clinical investigation subject administered a pharmaceutical product and which does not necessarily have a causal relationship with this treatment." An adverse event can, therefore, be any unfavorable and unintended sign, symptom, or disease temporally associated with the use of a medicinal (investigational) product, whether or not considered related to the medicinal (investigational) product.

AEs include any of the following:

- Worsening (change in nature, severity or frequency) of conditions present at the onset of the trial
- Subject deterioration due to the primary illness
- Intercurrent illnesses
- Drug interactions
- Events related or possibly related to concomitant medications
- Changes of vital signs, as well as significant shifts from baseline within the range of normal, which the Investigator considers to be clinically significant

Adverse Drug Reaction

In the pre-approval clinical experience with a new medicinal product or its new usage, particularly as the therapeutic dose(s) may not be established, an adverse drug reaction is defined as:

All noxious and unintended responses to a medicinal product related to any dose should be considered adverse drug reactions (ADR).

Unexpected Adverse Drug Reaction

An unexpected ADR is:

An adverse drug reaction, the nature or severity of which is not consistent with the applicable product information, also known as reference safety information. The reference safety information is the package insert of the individual drug.

Serious Adverse Event/Serious Adverse Drug Experience

During clinical investigations, serious AEs may occur, if the event is suspected to be drug-related, the event may be significant enough to lead to important changes in the way the medicinal product is developed (*e.g.*, change in dose, population, needed monitoring, consent forms). This is particularly true for reactions, which, in their most severe forms, threaten life or function.

A serious AE (SAE) or serious adverse drug experience (SADE) is any untoward medical occurrence that:

- Results in death
- Is life-threatening. 'Life-threatening" refers to an event in which the subject is at risk of death at the time of the event; it does not refer to an event which hypothetically might have caused death if it were more severe (ICH E6).
- Requires inpatient hospitalization or prolongation of existing hospitalization
- Results in persistent or significant disability/ incapacity (as per reporter's opinion)
- Is a congenital anomaly/birth defect
- Is another medically important condition. Important medical conditions that may not result in death, be life-threatening or require hospitalization may be considered as SAEs or SADEs when, based upon appropriate medical judgment, they may jeopardize the subject or may require intervention to prevent one of the outcomes listed in the definition above. Examples of such events are intensive treatment in an emergency room or at home for allergic bronchospasm; blood dyscrasias or convulsions that do not result in hospitalization; or development of drug dependency or drug abuse [Code of Federal Regulations Title 21, Volume 5, 21CFR312.32, revised April 1, 2006].

Please note: Serious is not synonymous with severe. An event may be severe (e.g., severe headache) but still be of minor medical significance. Serious refers to an event that poses a threat to the subject's life or functioning.

Assigning Severity to an Adverse Event

Mild: Causing no limitation of usual activities,

the subject may experience slight discomfort.

Moderate: Causing some limitation of usual activities,

the subject may experience annoying discomfort.

Severe: Causing inability to carry out usual activities;

the subject may experience intolerable discomfort or pain.

Assigning Relationship of Adverse Event to Study Drug (Causality)

The Principal Investigator will determine the relationship of each SAE to study drug (i.e., causality) by using the classification criteria 'not related,' 'possibly related', or 'probably related'. Descriptions of the three classification categories are as follows:

Not Related

Exposure to study drug has not occurred; administration of study drug and the adverse event are not reasonably related in time; or the SAE is considered by the Investigator to be due to a pre-existing condition, a known manifestation of the target disease, a recurrent condition, or is likely explained by environmental or diagnostic therapeutic factors or was pre-existing and did not deteriorate.

Possibly Related

The SAE occurred during or within a reasonable period of time after administration of the study drug, or a preexisting event worsened within an appropriate period of time after administration of study drug, but the SAE

could be explained equally well by factors or causes other than exposure to the study drug. This category will also be used if there is a lack of information, or insufficient or conflicting evidence exists for classifying the causality of the SAE.

Probably Related

The SAE occurred during or within a reasonable period of time after administration of the study drug or a preexisting event worsened within an appropriate period of time after administration of study drug, and at least one of the following criteria is applicable:

- the event could not be explained by the clinical condition or history of the subject, environmental or toxic factors, or other diagnostic or therapeutic measures;
- the event was an expected ADR associated with study treatment or a class-labeled drug effect;
- the SAE subsided or disappeared after withdrawal or dose reduction of study treatment; or
- the SAE recurred after re-exposure to study treatment.

Adverse Event Recording

Each adverse event occurring to a subject, either spontaneously revealed by the subject or observed by the Investigator, whether believed to be related or unrelated to the study drug, must be recorded on the AE Case Report Form and the subject's file.

Adverse Event Reporting

